**2.3.1.5 (For arms in the ARVs with Postpartum Contraceptives study arm group)**

Objective:

To describe the concentrations of ethinyl estradiol, etonogestrel and other progestins in women using hormonal contraceptives and selected ARV drugs as compared to historical controls not using those ARV drugs.

Outcome measure: Plasma concentrations of contraceptives.

Note: No historical controls were provided by team pharmacologists and no analysis was done for this comparison. This will be noted in the ClinicalTrials.gov description of the analysis.

## 2.3.2 Secondary Objectives and Outcome Measures

### 2.3.2.1 (For arms in the ARVs without TB Treatment, ARVs with First Line TB Treatment, or Second Line TB Treatment for Drug-Resistant TB with or without ARVs study arm groups).

Objective:

To compare ARV and TB drug concentrations in plasma from cord blood with those in maternal plasma at the time of delivery.

Outcome measure: ARV and TB drug cord blood/maternal plasma concentration ratio at delivery

### 2.3.2.2 To assess plasma protein binding of highly bound ARV drugs during pregnancy and postpartum\*.

### 2.3.2.3 To assess ARV concentrations and HIV RNA/DNA concentrations in vaginal secretions among pregnant and postpartum and compare to simultaneous plasma concentrations\*.

### 2.3.2.4 To explore genetic sources for variability in ARV and TB drug exposure in pregnant women and their infants\*.

### 2.3.2.5 (For all study arms).

Objective:

To describe maternal and infant safety and clinical outcomes.\*

Outcome measure: N (%) of:

- 1) Adverse events (AE) of grade 3 or higher;
- 2) Infant neurological events of grade 1 or higher;
- 3) Adverse pregnancy outcomes including preterm birth, low birth weight, and fetal demise;
- 4) Congenital anomalies;
- 5) Infant HIV infection status as defined according to the most current IMPAACT definition

### 2.3.2.6 (For arms in the ARVs without TB Treatment, ARVs with First Line TB Treatment, or Second Line TB Treatment for Drug-Resistant TB with or without ARVs study arm groups).

Objective:

To describe the neonatal elimination of selected ARV and TB drugs acquired across the placenta after maternal dosing during pregnancy.

Outcome measure: Infant washout half-life and concentration of drug after birth (if infants meet the criteria specified in Protocol Section 4.4 for washout PK sampling)

2.3.2.7 To describe pharmacokinetics of ARV drug combinations in HIV-infected women on second line TB treatment\*.

\* Note: These 5 secondary objectives were intended to be exploratory, and will be considered as “Other study objectives”. Therefore, this SAP will not include the outcome measures/analysis contents related to these objectives.

## **2.4 Overview of Sample Size Considerations**

The sample size calculations will be based on assessing whether therapeutic dosing regimens for the study drugs produce adequate drug exposure during pregnancy as compared to historical data from non-pregnant adults.

Each study arm will enroll a minimum of 12 women and have a target enrollment of 25 women with evaluable 3rd trimester PK data for ARV and TB arms, or evaluable postpartum PK data for oral contraceptive arms. Women who do not have evaluable data will be replaced. Enrollment may be restricted or adjusted so that evaluable 2nd trimester PK data are obtained from at least 12 women. The sample size for an arm may also be increased if additional mothers and infants need to be enrolled to obtain evaluable infant washout PK data. Thus, the total number of participants enrolled per arm may be larger than 25 if women need to be replaced due to non-evaluable data, if additional women need to be enrolled to obtain 2nd trimester PK data, if additional mothers and infants need to be enrolled to obtain infant washout PK data and/or if additional women need to be enrolled to obtain enough second line TB drug data. When combined enrollment in the increased dose darunavir arms reaches 25 participants, the PK data will be evaluated to determine if the data for these arms can be combined and whether enrollment of additional participants in these arms should continue. The actual sample size will be based on the determination of PK exposure parameters, and whether or not the current dose provides adequate drug exposure to pregnant women.

## **2.5 Overview of Formal Interim Monitoring**

Interim PK exposure monitoring during pregnancy (for ARVs only):

Based on data regarding the ARV drugs presently under study, the major concern is that the ARV drug exposure in pregnant women will be lower than that of the non-pregnant population, and the interim PK exposure monitoring rules are designed to detect this scenario quickly. In each study arm, at any time after a minimum of 12 participants have been enrolled, if six or more pregnant women have the third- trimester PK exposure parameter below the 10th percentile for the non-pregnant population, the study team will evaluate the adequacy of drug exposure in that arm, and with the agreement of the medical officers, determine whether enrollment to that arm should continue. The exact 80% confidence limits for 6 participants with low drug exposure out of a total of 25 are (0.13, 0.38), which exclude 10% and indicate strong evidence that the distribution of the PK parameter of interest for the pregnant women is different from that for the non-pregnant women. If a statistical difference appears to be clinically important, then enrollment into that study arm will stop and a new study arm at a higher dose will be developed, if feasible.

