## **2 Study Overview**

### **2.1 Overview of Study Design**

P1026s is a Phase IV, prospective pharmacokinetic (PK) study to evaluate the pharmacokinetics of selected currently prescribed antiretroviral (ARV) medicines when used alone or with tuberculosis (TB) medicines during pregnancy or with postpartum hormonal contraceptives in HIV-infected pregnant and postpartum women. The washout PK of transplacentally acquired ARV and TB drugs will be studied in the infants born to study mothers who enter the study during pregnancy. HIV-uninfected pregnant women receiving TB treatment (first line or second line) will also be enrolled to serve as a control group to evaluate the interaction between TB and ARV drugs in pregnant women.

Study Arm Groups (see arm details in Section 7 Attachment 1 and Protocol Schema):

- ARVs without TB Treatment (10 Arms)
- ARVs with First Line TB Treatment (2 Arms - one for each ARV drug)
- No ARVs with First Line Tuberculosis Treatment (1 Arm)
- Second Line TB Treatment for Drug-Resistant TB with or without ARVs (1 Arm)
- ARVs with Postpartum Contraceptives (4 Arms)

There is no randomization and stratification. Each study arm will enroll a minimum of 12 women and have a target enrollment of 25 women with evaluable 3rd trimester PK data in the ARV and TB arms, or evaluable postpartum PK data in the contraception arms. Enrollment may be restricted or adjusted so that 2nd trimester PK data are collected from at least 12 women. When combined enrollment in the increased dose darunavir arms reach 25 participants, the PK data will be evaluated to determine if the data for these arms can be combined and whether enrollment of additional participants in these arms should continue. Sample size for an ARV or TB drug arm may be increased if additional infants need to be enrolled to collect infant washout PK data. The

sample size of the second line TB drug arm may be increased above 25 to obtain additional data for less commonly used second line TB drugs.

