### 3 General Considerations

Each analysis will include all participants with evaluable data for that analysis. A participant's data will be deemed unevaluable by a protocol pharmacologist for a specific analysis if they do not have adequate pharmacokinetic evaluations to determine the pharmacokinetic exposure parameter of interest for that analysis. For safety analyses, a participant's data will be deemed unevaluable only if the participant did not receive any amount of the drug under study.

Visit windows are defined in Protocol Appendix IA-ID and Appendix II for mothers and infants, respectively. Specifically, maternal HIV RNA and CD4 tests for each PK visit allow a window of  $\pm$  8 weeks around the PK evaluation date. For mothers of non-contraceptive arms, entry visit (which may occur at the 2P or 3P visit) is the baseline; for mothers of contraceptive arms, entry visit (2-12 weeks postpartum) is the baseline. For infants, day of birth is defined as Day 0; birth visit is the baseline.

Continuous variables (e.g. gestational age) will be summarized with descriptive statistics (mean, median, standard deviation, interquartile range, and range). Categorical data (e.g. sex) will be summarized with frequencies and percentages for each category. Reports may also include listings with details related to safety events.

In this study, each arm will enroll independently. Final analysis for each arm will be done when that arm completes follow-up and PK assays have been run. Each study arm will have a separate Final Analysis Report (unless the team decides to combine analyses across certain arms).

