
*Stage 1 analysis for the TB drugs will not be done in real time and will only be done when batched PK data are available (unlike the Stage I analysis for ARVs).  **This comparison may have a smaller sample size than 25 because some women may complete their TB treatment before the postpartum PK visit.  #Interim AUC monitoring (Stage 1 analysis) is not done for these arms (only done during pregnancy).
			

In Stage 1, an individual woman’s PK exposure parameter during pregnancy will be compared in real time to the 10th percentile for that PK exposure parameter for that drug from a non-pregnant population, and the woman and her clinical provider will be notified if the woman’s value is below the 10th percentile. If there is strong evidence that the true percentage of pregnant women having the PK exposure parameter below the 10th percentile for the non-pregnant population is greater than 10%, the study team will evaluate whether to stop enrollment early and whether to recommend that additional study of the drug/drug combination is necessary.

Stage 2 for the ARV drugs taken during pregnancy will implement a repeated measures design, in which antepartum and postpartum measurements from each woman will be compared. This stage requires a minimum of 12 participants in each arm to have postpartum PK measurements. If less than 12 participants out of the 25 in any arm have postpartum measurements, more participants will be enrolled in that arm until the minimum postpartum measurement number of 12

is reached. The comparisons will be made at the within-participant level, using the Wilcoxon signed rank test to assess whether there is a statistically significant difference in the PK exposure parameter in the pregnant versus non-pregnant conditions. 90% confidence limits for the geometric mean ratio of the PK exposure parameter in the pregnant versus non-pregnant conditions will also be calculated to describe the range of values that are consistent with the observed data and help the Protocol Team assess whether there is a clinically important difference in exposure in the pregnant versus non-pregnant conditions.

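### Does the fixed trigger of six low third-trimester values need rescaling if an ARV arm grows beyond 25 women?

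*SAP*

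**What the plan says.** Section 2.5 of the SAP covers ARV exposure in pregnancy and gives the trigger as an absolute number: "In each study arm, at any time after a minimum of 12 participants have been enrolled, if six or more pregnant women have" a third-trimester value under the 10th percentile for non-pregnant people, the team evaluates that arm and, with the medical officers' agreement, decides whether enrollment goes on. The number six is supported by one calculation: "The exact 80% confidence limits for 6 participants with low drug exposure out of a total of 25 are (0.13, 0.38"), which lies above 10%. A further condition governs stopping: "If a statistical difference appears to be clinically important, then enrollment into that study arm will stop".

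Section 2.4 sets a "target enrollment of 25 women with evaluable 3rd trimester PK data for ARV and TB arms", and section 3 adds "Each analysis will include all participants with evaluable data for that analysis". The denominator for the rule is therefore women with evaluable third-trimester PK, not everyone enrolled.

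Three provisions can take that denominator above 25:
- Infant washout (section 2.1): "Sample size for an ARV or TB drug arm may be increased if additional infants need to be enrolled".
- Second-trimester data, listed with washout in section 2.4: "if additional women need to be enrolled to obtain 2nd trimester PK data, if additional mothers and infants need to be enrolled".
- Postpartum data (section 4): "If less than 12 participants out of the 25 in any arm have postpartum measurements, more participants will be enrolled in that arm", until 12 have them.

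The SAP states no maximum. Its one checkpoint at 25 women concerns the increased-dose darunavir arms. Section 4 makes any discussion of early stopping depend on strong evidence that the true low-exposure percentage exceeds 10%.

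**The concern.** A fixed count means different things at different sample sizes. Six of 25 is 24% and six of 40 is 15%. Section 2.5 shows that six is convincing at 25 and then applies it without limit to arms that may grow. If the sixth low value arrives late in a large arm, the count in section 2.5 is met while the interval that justified it no longer excludes 10%, so the trigger and the evidence standard in section 4 part company.

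The count can only rise, so the chance of reaching six by luck grows with every woman added. An arm enlarged for reasons unrelated to exposure, such as infant washout sampling, could be sent to review, and perhaps closed, although exposure in pregnancy is no lower than in non-pregnant adults.

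**Working it through.** **Inputs.** From section 2.5: trigger count 6, monitoring from 12 women, reference proportion 0.10, exact two-sided 80% limits (10% in each tail). From section 2.4: target of 25 women with evaluable third-trimester PK.

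**Reproducing the SAP's figure.** The exact (Clopper-Pearson) limits for x low values among n women are
- lower = Beta quantile(0.10; x, n − x + 1)
- upper = Beta quantile(0.90; x + 1, n − x)

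For x = 6, n = 25: Beta quantile(0.10; 6, 20) = 0.1312 and Beta quantile(0.90; 7, 19) = 0.3833. These round to the stated 0.13 and 0.38.

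**Same method, other sizes, x = 6.** The lower limit exceeds 0.10 exactly when P(X ≥ 6 | n, 0.10) is below 0.10. Because the count never falls, that tail probability is also the cumulative chance of having triggered by n under continuous monitoring at a true low rate of 10%.

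| n | Exact 80% lower limit | Chance of having triggered, true rate 10% |
|---|---|---|
| 12 | 0.288 | 0.0005 |
| 20 | 0.166 | 0.011 |
| 25 | 0.131 | 0.033 |
| 30 | 0.109 | 0.073 |
| 32 | 0.1016 | 0.094 |
| 33 | 0.0984 | 0.106 |
| 35 | 0.0926 | 0.132 |
| 40 | 0.0807 | 0.206 |

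Six excludes 10% at every size from 12 to 32 and fails from 33. At 25 it is stricter than the standard requires: five of 25 has a lower limit of 0.1006.

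**How an arm could reach 33.** The completion rates below are assumptions; the SAP gives none.
- *Postpartum route.* Enrollment passes 32 only if at most 11 of 32 women give a postpartum profile. P(Binomial(32, q) ≤ 11) is 0.323 for q = 0.40, 0.055 for q = 0.50 and 0.003 for q = 0.60.
- *Second-trimester route.* If k of the first 25 women have such data and each added woman supplies one profile, the arm ends at 25 + (12 − k). Reaching 33 needs 12 − k ≥ 8, so k ≤ 4.
- *Washout route.* No number is stated, so nothing can be computed.

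**What rescaling would do.** Keep six up to n = 32 and use seven for n = 33 to 40 (lower limits 0.1221 at 7/33 and 0.1001 at 7/40). Chance of having triggered, looking after every woman from 12:

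| True low rate | By n | Fixed six | Rescaled |
|---|---|---|---|
| 10% | 35 | 0.132 | 0.098 |
| 10% | 40 | 0.206 | 0.125 |
| 20% | 35 | 0.728 | 0.657 |
| 20% | 40 | 0.839 | 0.744 |
| 30% | 40 | 0.991 | 0.980 |

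At n = 40 rescaling removes 0.2063 − 0.1247 = 0.0816 of false triggers and gives up 0.8387 − 0.7435 = 0.0952 of detection at a true 20%.

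**Size of the avoidable excess.** Suppose every arm that passes 32 by the postpartum route goes on to 40. The added chance of a false trigger is then 0.0551 × 0.0816 = 0.0045 at 50% completion and 0.3233 × 0.0816 = 0.026 at 40%.

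**The case for a change.** The strongest case for a change is that the SAP supplies its own standard, an exact 80% interval that excludes 10%, and then fixes a count that breaks this standard in arms it expressly allows. The crossover at 33 is exact under the named method. Section 2.5 does not tell the team to recompute the interval at the size actually reached. The remedy would be cheap: a sentence and a short table, with nothing altered at 32 women or fewer. A team that prefers sensitivity could keep six and report the interval at the actual size.

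The arithmetic stands, and so does the observation that the SAP caps neither the arm size nor the rule. The need for a change does not follow. Rescaling is a choice between false alarms and detection, and section 2.5 says that the rule is meant to pick up low exposure quickly. The rescaled rule does not have a clean error rate either: its false-trigger probability still reaches 12.5% by 40 women, because a fixed-sample interval is being applied to repeated looks. Reporting the interval at the actual size is sensible, but a team asked to judge whether a statistical difference exists would compute it anyway.

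**Conclusion.** No change is needed. At the target of 25, and up to 32 women with evaluable third-trimester PK, six low values meet the SAP's own standard, with a false-trigger probability of 3.3% by 25 and 9.4% by 32. Above 32 the shortfall begins small: the lower limits at 33 and 34 (0.0984 and 0.0954) still round to 0.10 at the two decimals the SAP uses. It becomes material only towards 40, where the limit is 0.081 and the false-trigger probability 20.6%.

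Even there, the count alone stops nothing. It opens an evaluation that involves the medical officers. Closing an arm further requires a statistical difference judged clinically important, and section 4 asks for strong evidence of a rate above 10%. A team holding 6 of 33 would see an interval of 0.098 to 0.297 and would not have that evidence. The expected cost is an occasional unneeded review, in exchange for better detection when exposure really is low.

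This rests on two points. The denominator is women with evaluable third-trimester data, so replacing non-evaluable women does not raise it. Growth to 33 is permitted but nowhere planned, and the completion rates used above are assumed. The SAP's version history says that statisticians have followed the protocol's Statistical Considerations section since 2003. That text was not available for this review and may already deal with larger arms.

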### 3 General Considerations

Each analysis will include all participants with evaluable data for that analysis. A participant's data will be deemed unevaluable by a protocol pharmacologist for a specific analysis if they do not have adequate pharmacokinetic evaluations to determine the pharmacokinetic exposure parameter of interest for that analysis. For safety analyses, a participant's data will be deemed unevaluable only if the participant did not receive any amount of the drug under study.

Visit windows are defined in Protocol Appendix IA-ID and Appendix II for mothers and infants, respectively. Specifically, maternal HIV RNA and CD4 tests for each PK visit allow a window of  $\pm$  8 weeks around the PK evaluation date. For mothers of non-contraceptive arms, entry visit (which may occur at the 2P or 3P visit) is the baseline; for mothers of contraceptive arms, entry visit (2-12 weeks postpartum) is the baseline. For infants, day of birth is defined as Day 0; birth visit is the baseline.

Continuous variables (e.g. gestational age) will be summarized with descriptive statistics (mean, median, standard deviation, interquartile range, and range). Categorical data (e.g. sex) will be summarized with frequencies and percentages for each category. Reports may also include listings with details related to safety events.

In this study, each arm will enroll independently. Final analysis for each arm will be done when that arm completes follow-up and PK assays have been run. Each study arm will have a separate Final Analysis Report (unless the team decides to combine analyses across certain arms).

### 4 Analysis Approaches

For the PK related objectives, this SAP defines the descriptive PK data summaries and PK comparisons to be done by the protocol statisticians. The pharmacokinetic parameters will be calculated by the protocol pharmacologists, and their derivation/analysis will be defined in a separate Pharmacokinetic SAP.

If PK concentration values are missing due to below the level of quantification (BLQ), they will be set to  $\frac{1}{2}$  the lower limit of quantitation (LLOQ) for calculations. If an entire concentration-time profile is BLQ, the profile will be reported separately and excluded from the summary PK analysis. The comparisons to be performed to address the primary objectives for certain arms will vary according to type of drug and timing of sampling. Table 1 summarizes these comparisons for each type of drug.

Table 1: Pharmacokinetic Parameter Comparisons to be Performed for Each Type of Drug for the Primary Objectives

Type of Drug	Analysis Stage	Description of Pharmacokinetic Parameter Comparison	Type of Comparison
ARV without TB Drugs	Stage 1	Antepartum PK parameter vs. 10 th percentile from external, non-pregnant population	Between-participant
	Stage 2	Antepartum vs. postpartum PK parameters	Within-participant
ARV with First Line TB Drugs	Stage 1	Antepartum ARV PK parameter vs. 10 th percentile from non-pregnant population	Between-participant
	Stage 2	Antepartum vs. postpartum ARV PK parameters	Within-participant
	Stage 3	ARV PK parameter with TB drugs vs. ARV PK parameter without TB drugs in previous P1026s arm	Between-participant
First Line TB drugs with ARVs (HIV+) and First Line TB drugs without ARVs (HIV-)	Stage 1*	Antepartum TB drug PK parameter vs. 10 th percentile from non-pregnant population	Between-participant
	Stage 2	Antepartum vs. postpartum TB drug PK parameter, separately for HIV+ and HIV-	Within-participant**
	Stage 3	TB drug PK parameter with ARV (HIV+) vs. TB drug PK parameter without ARV (HIV-)	Between-participant
Second Line TB drugs with or without ARVs	Stage 2	Antepartum vs. postpartum TB drug PK parameters	Within-participant**
ARV with Contraceptives #	Stage 2	Postpartum ARV PK parameter before vs. after starting contraceptives	Within-participant
Contraceptives with ARVs	Stage 3	Postpartum contraceptive concentration with ARV vs. external historical controls not receiving ARV	Between-participant

*Stage 1 analysis for the TB drugs will not be done in real time and will only be done when batched PK data are available (unlike the Stage I analysis for ARVs).  **This comparison may have a smaller sample size than 25 because some women may complete their TB treatment before the postpartum PK visit.  #Interim AUC monitoring (Stage 1 analysis) is not done for these arms (only done during pregnancy).
			

In Stage 1, an individual woman’s PK exposure parameter during pregnancy will be compared in real time to the 10th percentile for that PK exposure parameter for that drug from a non-pregnant population, and the woman and her clinical provider will be notified if the woman’s value is below the 10th percentile. If there is strong evidence that the true percentage of pregnant women having the PK exposure parameter below the 10th percentile for the non-pregnant population is greater than 10%, the study team will evaluate whether to stop enrollment early and whether to recommend that additional study of the drug/drug combination is necessary.

Stage 2 for the ARV drugs taken during pregnancy will implement a repeated measures design, in which antepartum and postpartum measurements from each woman will be compared. This stage requires a minimum of 12 participants in each arm to have postpartum PK measurements. If less than 12 participants out of the 25 in any arm have postpartum measurements, more participants will be enrolled in that arm until the minimum postpartum measurement number of 12

is reached. The comparisons will be made at the within-participant level, using the Wilcoxon signed rank test to assess whether there is a statistically significant difference in the PK exposure parameter in the pregnant versus non-pregnant conditions. 90% confidence limits for the geometric mean ratio of the PK exposure parameter in the pregnant versus non-pregnant conditions will also be calculated to describe the range of values that are consistent with the observed data and help the Protocol Team assess whether there is a clinically important difference in exposure in the pregnant versus non-pregnant conditions.

For the ARV drugs being taken with first line TB drugs, in addition to Stages 1 and 2, a third stage of analysis (Stage 3) will be performed which will compare the ARV PK exposure with first line TB drugs to the PK exposure for these ARVs without first line TB drugs in previously evaluated arms of the P1026s study. This analysis will involve a between-participants comparison of PK exposure parameters using the two-sample Wilcoxon rank sum test. 90% confidence limits for the geometric mean ratio of the PK exposure parameters in the two groups of women will also be calculated.

For the first line TB drugs, a Stage 1 analysis similar to that described above will be performed but only after completion of the concentration assays following batch shipment. Since the TB drug samples will not be shipped and assayed in real time and the duration of TB drug treatment is time limited, the participant may no longer be receiving the TB drug being studied when the TB drug assay results become available. The PK analysis for the first line TB drugs will also include the Stage 2 approach described above, in which a within-participants comparison of TB drug PK exposure during pregnancy and postpartum will be performed, separately for HIV-infected and HIV-uninfected women in each study arm. Note that the sample size for this comparison may be less than the desired 25 evaluable women if some women complete their TB medication course before the postpartum visit where the PK sampling will be done. In addition, a Stage 3 between-participants comparison of first line TB drug PK exposure in HIV-infected versus HIV-uninfected women will be performed (using the two-sample Wilcoxon rank sum test) to assess whether exposure to first line TB drugs differs with vs. without concomitant ARV drug use and presence of HIV infection. Note that if a significant difference is observed in the between-participants analysis, it will not be possible to determine whether this difference is due to ARV use or HIV infection.

For the second line TB drugs, the PK analysis will use the Stage 2 approach described above, in which a within-participants comparison of TB drug PK exposure during pregnancy and postpartum will be performed. Note that the sample size for these comparisons may be less than the desired 25 evaluable women per drug because the inclusion criteria for this study arm only require that women are receiving at least two of the specified second line TB drugs, and because some women may complete their TB medication course before the postpartum visit where the PK sampling will be done. It may or may not be possible to perform a Stage 3 between-participants comparison of second line TB drug PK exposure in HIV-infected versus HIV-uninfected women; depending on the number of women receiving each TB drug, it may be necessary to combine data from HIV-infected and HIV-uninfected women.

For the ARV drugs being taken with postpartum contraceptives, the Stage 1 analysis above will not be performed (the Stage 1 analysis will only be done for ARV during pregnancy). A within-participants analysis similar to the Stage 2 analysis described above will be performed, except

that the ARV PK exposure parameters before versus after starting contraceptives will be compared (instead of during pregnancy versus postpartum).

For the contraceptives, a Stage 3 analysis will be performed that will compare the contraceptive concentrations observed in P1026s women receiving a protease inhibitor to data from historical controls not receiving ARVs, as reported in the available literature.

For analyses of PK secondary objectives, descriptive statistics (mean, median, standard deviation, interquartile range, and range) will be tabulated for PK outcome measures. If most infant washout PK data are below the BLQ for a given study arm, the pharmacologist may determine that the analysis report should not include an infant washout PK data summary (this will be noted in the report).

For the secondary objectives related to safety and clinical outcomes, adverse events and other safety outcome measures will be tabulated, and descriptive statistics (mean, median, standard deviation, interquartile range, and range) will be calculated for CD4 and HIV-1 RNA measurements (for HIV-infected participants only).

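### As written, the half-LLOQ rule for BLQ samples also reaches infant washout half-life, and would bias it if substituted values enter the slope

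*SAP*

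**What the plan says.** SAP Section 4 gives one BLQ rule. "If PK concentration values are missing due to below the level of quantification (BLQ), they will be set to" one half of "the lower limit of quantitation (LLOQ) for calculations". It does not list which calculations are meant. It makes one exception: "If an entire concentration-time profile is BLQ, the profile will be reported separately and excluded from the summary PK analysis". Infant samples, trailing samples and slope-based parameters are not exempted.

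Just before the rule, the same section limits this SAP to the statisticians' summaries and comparisons, and adds: "The pharmacokinetic parameters will be calculated by the protocol pharmacologists, and their derivation/analysis will be defined in a separate Pharmacokinetic SAP".

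Section 2.3.2.6 names the outcome: "Infant washout half-life and concentration of drug after birth". It is not one of the starred objectives that the SAP sets aside as exploratory, and Section 5 lists a half-life summary among the report contents. The analysis is descriptive: Section 4 says that summary statistics "will be tabulated for PK outcome measures".

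Two other provisions bear on this. In Section 4, "If most infant washout PK data are below the BLQ for a given study arm, the pharmacologist may determine" that the arm's report should omit the infant washout summary. Section 3 lets a pharmacologist declare data unevaluable when sampling is inadequate for the parameter in question.

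**The concern.** Washout sampling follows a falling concentration, so BLQ results tend to collect at the end of the profile, where a sample has much leverage on a log-linear slope. Substitution gives all of them the same value. Two substituted values in a row have slope zero, while the true concentration goes on falling. Estimated half-life then depends partly on the assay limit and the time of the last sample, not only on the infant's elimination of the drug.

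At stake is a reported neonatal outcome. A drug that clears quickly could be described as persisting for a day or more after birth.

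**Working it through.** **What can be checked.** The documents available for review give no infant half-life, LLOQ, infant sampling times or BLQ fraction, so there is no figure of the plan's to reproduce. The check shows what the rule would do if it were applied to the half-life fit.

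**Assumed inputs.** Four samples, at 6, 24, 48 and 72 h or at 6, 24, 48 and 168 h; birth level C0 of 20, 50 or 100 times the LLOQ; mono-exponential decline; least squares through all four samples, substituted ones included. The last of these is an assumption too, and the result depends on it.

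**Formulas.** With LLOQ = 1 and true half-life T:
- C(t) = C0 × 2^(−t/T), and any value below 1 is replaced by 0.5.
- With base-2 logs, fitted half-life = −Σd² / Σ(d × log2 C), where d is the sample time minus the mean sample time.

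**Example 1, inflation.** T = 8 h, C0 = 50, last sample at 168 h.
- True concentrations are 29.73, 6.25, 0.781 and 0.00002. The last two are BLQ, so the logs used are 4.894, 2.644, −1 and −1.
- Mean time is 61.5 h; d = −55.5, −37.5, −13.5, 106.5; Σd² = 16,011.
- Σ(d × log2 C) = −271.61 − 99.14 + 13.5 − 106.5 = −463.75.
- Fitted half-life = 16,011 / 463.75 = 34.5 h against a true 8 h.

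**Example 2, the opposite direction.** T = 12 h, C0 = 50, last sample at 72 h.
- True concentrations are 35.36, 12.5, 3.125 and 0.781. Only the last is BLQ, and 0.5 is lower than its true value.
- Mean time is 37.5 h; d = −31.5, −13.5, 10.5, 34.5; Σd² = 2,475.
- Σ(d × log2 C) = −162.03 − 49.19 + 17.26 − 34.5 = −228.46.
- Fitted half-life = 2,475 / 228.46 = 10.8 h against a true 12 h.

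**All settings.** Fitted half-life in hours, without noise, with the number of BLQ samples in brackets:

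| Last sample | True half-life | C0 = 20 | C0 = 50 | C0 = 100 |
|---|---|---|---|---|
| 72 h | 8 h | 14.1 (2) | 10.5 (2) | 9.4 (1) |
| 72 h | 12 h | 13.5 (1) | 10.8 (1) | 12.0 (0) |
| 72 h | 24 h | 24.0 (0) | 24.0 (0) | 24.0 (0) |
| 168 h | 8 h | 47.0 (2) | 34.5 (2) | 27.7 (1) |
| 168 h | 12 h | 39.0 (1) | 29.1 (1) | 24.4 (1) |
| 168 h | 24 h | 32.8 (1) | 25.4 (1) | 21.8 (1) |

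Fitting only the quantifiable samples returns the true value exactly in every cell. With 25% lognormal noise, it gives medians of 8.0 to 8.3 h for a true 8 h and 11.8 to 12.4 h for a true 12 h.

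**Direction.** A substituted last sample steepens the slope if its true value exceeds half the LLOQ and flattens it if the true value is lower. With samples at 6, 24, 54 and 168 h, C0 = 50 and only the last sample BLQ, true values of 0.95, 0.8, 0.5, 0.2 and 0.05 times the LLOQ give fitted-to-true ratios of 0.85, 0.89, 1.00, 1.23 and 1.59.

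**Relative size.** On the 168 h schedule at C0 = 50, true half-lives of 6, 8 and 12 h fit as 38.8, 34.5 and 29.1 h, which are ratios of 6.5, 4.3 and 2.4. The order is reversed.

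**One quantifiable sample.** T = 3 h, C0 = 50: 12.5 at 6 h, then BLQ at 24, 48 and 168 h. The substituted fit gives 62.1 h, from a slope set almost wholly by the substituted values. The data support only an upper bound, (24 − 6) / log2(12.5) = 18 / 3.644 = 4.9 h.

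**The case against.** The strongest objection is scope. The SAP confines itself to the statisticians' work and assigns parameter derivation to the pharmacologists under another plan. Half-life is a derived parameter, so the BLQ rule can fairly be read as covering concentration summaries only. This stands as far as it goes: nothing in the documents shows that substituted values enter a half-life fit. It does not remove the point, because the rule follows directly after that deferral, speaks of calculations without limit and names its only exception. If the Pharmacokinetic SAP handles BLQ samples differently, the two texts disagree and this one should say which governs. If it does not, the bias is real.

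A second objection is that safeguards exist. They are discretionary. The option to omit the washout summary needs most of an arm's data to be BLQ, whereas in the table one or two samples of four are enough to distort the estimate. The evaluability rule concerns adequacy of sampling and does not say how a BLQ value enters a slope. Neither deals with partly BLQ profiles as such.

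A third is that the large figures come from one assumed time point: moving the last sample from 168 h to 72 h cuts the 8 h result from 28–47 h to 9–14 h. That is correct, and it is why only a range can be given.

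A reader might also infer that the plan expects heavy BLQ data, or that comparisons between drugs would be corrupted. The first is only a contingency in the text ("If most infant washout PK data are below the BLQ for a given study arm"), and no between-drug comparison of half-life is planned.

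**Conclusion.** The concern holds conditionally. The BLQ rule as written extends to infant washout half-life, and applying it there would give a biased estimate. Two or more trailing BLQ samples would generally inflate half-life, most in relative terms for fast-clearing drugs. One BLQ last sample can push it either way, and profiles with no BLQ samples are unaffected.

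A reader might go further and conclude that the trial's infant half-lives are overstated. The documents do not support that. The derivation method lies in a plan that is not available, and the direction is not fixed (a true 12 h fits as 10.8 h in one setting).

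Under the assumed schedules and birth levels of 20 to 100 times the LLOQ, a true 8 h fits as about 9 to 14 h or 28 to 47 h, depending on whether the last sample is at 72 or 168 h. Sampling times, assay limit, birth levels and fitting method are all assumptions. The outcome is secondary and descriptive.

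**What to change.** In SAP Section 4, limit the half-LLOQ rule for infant washout to concentration summaries, and agree the following wording with the Pharmacokinetic SAP so that the two plans match:

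> Half-LLOQ substitution is not used to estimate infant washout half-life. Half-life is estimated from quantifiable samples, with BLQ samples treated as left-censored or trailing BLQ samples dropped. Infants with fewer than two quantifiable samples are counted as not estimable. Where exactly one sample is quantifiable and a later one is BLQ, an upper bound may be reported.

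The authors should choose one of the two BLQ treatments in advance. Profiles that are BLQ throughout stay excluded and separately reported, as the SAP already provides; no bound can be formed for them.

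The cost is a short addition to the text and minor programming. Fewer infants will have a point estimate, so the report should give the number not estimable beside the half-life summary.
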